# ii. LIST OF ABBREVIATIONS

AE	Adverse Event
AKI	Acute Kidney Injury
API	Associate Principal Investigator
AMR	Anti-Microbially Resistant/Anti-Microbial Resistance
AR	Adverse Reaction
CI	Chief Investigator
cIAI	Complicated Intra-abdominal infection
CCI	Comprehensive Complications Index
C. difficile	Clostridium difficile
CPE	Carbapenemase producing Enterobacteriaceae
CRF	Case Report Form
CTIMP	Clinical Trial of Investigational Medicinal Product
СТU	Clinical Trials Unit
DMEC	Data Monitoring and Ethics Committee
eCRF	Electronic Case Report Form
ESBL	Extended spectrum beta-lactamases
GCP	Good Clinical Practice
HEAP	Health Economic Analysis Plan
HRA	Health Research Authority
ICH	International Conference on Harmonisation of technical requirements for registration of pharmaceuticals for human use
ICU	Intensive Care Unit
ISF	Investigator Site File (This forms part of the TMF)
ISRCTN	International Standard Randomised Controlled Trials
ІТТ	Intention-to-Treat
LTHT	Leeds Teaching Hospitals Trust

The EXTEND Trial protocol ISRCTN no. 72819021

MAR	Missing at Random
MCA	Mental Capacity Act
MHRA	Medicines and Healthcare products Regulatory Agency
MRSA	Meticillin resistant Staphylococcus aureus
NHS R&D	National Health Service Research & Development
NIHR	National Institute for Health and Care Research
PI	Principal Investigator
PIS	Participant Information Sheet
QALY	Quality Adjusted Life Year
RCT	Randomised Control Trial
REC	Research Ethics Committee
SAE	Serious Adverse Event
SAP	Statistical Analysis Plan
SAR	Serious Adverse Reaction
SOP	Standard Operating Procedure
SmPC	Summary of Product Characteristics
SUSAR	Suspected Unexpected Serious Adverse Reaction
TMF	Trial Master File
TMG	Trial Management Group
TSC	Trial Steering Committee
UoL	University of Leeds
VRE	Vancomycin resistant Enterococcus
YTU	York Trials Unit

# iii. TRIAL SUMMARY

Trial Title	The EXTEND trial: Fixed-extended-dura	ation antibiotics (28 days) compared
	to standard care antibiotic durations in adult patients with complicated intra-	
	abdominal infection and their impact on treatment failure-a phase III	
	multicentre, open label, two-arm, parallel group, pragmatic, randomised	
	controlled trial with internal pilot	
Short title	The EXTEND trial: EXTENDed antibiotic durations compared to standard	
	antibiotic durations for patients with complicated intra-abdominal infection	
Clinical Phase	Phase III	
Trial Design	Multicentre, open label, two-arm, paralle	el group, pragmatic, randomised
	controlled trial with internal pilot	
Trial Participants	Adult patients with complicated intra-ab	dominal infection
Planned Sample Size	1166	
Treatment duration	Standard care: Clinically decided antibiotic duration	
	Intervention care: A fixed-extended-dura	ation of 28 days antibiotics
	180 days	
Follow up duration	180 days	
Follow up duration Planned Trial Period	180 days 3 years 6 months (recruitment and follo	w-up)
Follow up duration Planned Trial Period	180 days 3 years 6 months (recruitment and follo Objectives	w-up) Outcome Measures
Follow up duration Planned Trial Period Primary	
 
180 days
 
3 years 6 months (recruitment and follor
 
Objectives
 
To compare the effectiveness of fixed
 
	w-up) Outcome Measures Treatment failure within 180 days of
Follow up duration Planned Trial Period Primary	
 
180 days
 
3 years 6 months (recruitment and follow
 
Objectives
 
To compare the effectiveness of fixed extended duration antibiotic treatment
 
	w-up) Outcome Measures Treatment failure within 180 days of randomisation
Follow up duration Planned Trial Period Primary	
 
180 days
 
3 years 6 months (recruitment and follow
 
Objectives
 
To compare the effectiveness of fixed extended duration antibiotic treatment with standard duration antibiotic
 
	w-up) Outcome Measures Treatment failure within 180 days of randomisation
Follow up duration Planned Trial Period Primary	
 
180 days
 
3 years 6 months (recruitment and follow
 
Objectives
 
To compare the effectiveness of fixed extended duration antibiotic treatment with standard duration antibiotic treatment with standard duration antibiotic treatment with respect to rate of
 
	w-up) Outcome Measures Treatment failure within 180 days of randomisation
Follow up duration Planned Trial Period Primary	
 
180 days
 
3 years 6 months (recruitment and follow
 
Objectives
 
To compare the effectiveness of fixed extended duration antibiotic treatment with standard duration antibiotic treatment with respect to rate of treatment failure in patients treated for
 
	w-up) Outcome Measures Treatment failure within 180 days of randomisation
Follow up duration Planned Trial Period Primary	
 
180 days
 
3 years 6 months (recruitment and follow
 
Objectives
 
To compare the effectiveness of fixed extended duration antibiotic treatment with standard duration antibiotic treatment with standard duration antibiotic treatment with respect to rate of treatment failure in patients treated for complicated intra-abdominal infection.
 
	w-up) Outcome Measures Treatment failure within 180 days of randomisation
Follow up duration Planned Trial Period Primary Secondary	
 
180 days
 
3 years 6 months (recruitment and follow
 
Objectives
 
To compare the effectiveness of fixed extended duration antibiotic treatment with standard duration antibiotic treatment with standard duration antibiotic treatment with respect to rate of treatment failure in patients treated for complicated intra-abdominal infection.
 
To compare the effectiveness of fixed
 
	w-up) Outcome Measures Treatment failure within 180 days of randomisation
Follow up duration Planned Trial Period Primary Secondary	
 
180 days
 
3 years 6 months (recruitment and follow
 
Objectives
 
To compare the effectiveness of fixed extended duration antibiotic treatment with standard duration antibiotic treatment with respect to rate of treatment failure in patients treated for complicated intra-abdominal infection.
 
To compare the effectiveness of fixed extended duration antibiotic treatment
 
	w-up) Outcome Measures Treatment failure within 180 days of randomisation
Follow up duration Planned Trial Period Primary Secondary	
 
180 days
 
3 years 6 months (recruitment and follow
 
Objectives
 
To compare the effectiveness of fixed extended duration antibiotic treatment with standard duration antibiotic treatment with standard duration antibiotic treatment failure in patients treated for complicated intra-abdominal infection.
 
To compare the effectiveness of fixed extended duration antibiotic treatment with standard duration antibiotic treatment
 
	w-up) Outcome Measures Treatment failure within 180 days of randomisation
Follow up duration Planned Trial Period Primary Secondary	
 
180 days
 
3 years 6 months (recruitment and follow
 
Objectives
 
To compare the effectiveness of fixed extended duration antibiotic treatment with standard duration antibiotic treatment with respect to rate of treatment failure in patients treated for complicated intra-abdominal infection.
 
To compare the effectiveness of fixed extended duration antibiotic treatment with standard duration antibiotic
 
	w-up) Outcome Measures Treatment failure within 180 days of randomisation
Follow up duration Planned Trial Period Primary Secondary	
 
180 days
 
3 years 6 months (recruitment and follow
 
Objectives
 
To compare the effectiveness of fixed extended duration antibiotic treatment with standard duration antibiotic treatment with standard duration antibiotic treatment failure in patients treated for complicated intra-abdominal infection.
 
To compare the effectiveness of fixed extended duration antibiotic treatment with standard duration antibiotic
 
1. Quality of life in patients treated for
 
	w-up) Outcome Measures Treatment failure within 180 days of randomisation

2. Treatment in terms of impact on an ordinal ranking outcome score	DOOR analysis
3. A range of secondary outcome measures (measured from day 0 to day 180)	Time to treatment failure Number and type of source control procedures
	Relapse of cIAI
	Number of episodes of treatment failure: Only one episode of treatment failure can occur within a 10-day period
	All-cause mortality (time to event)
	Length of hospital stay
	Re-admissions
	C. difficile infection
	Anti-microbial resistant (AMR) infections
	Days of antibiotic therapy (in-patient and outpatient, including anti-fungal therapy)
	Acute kidney injury (AKI)
	Complications
	Days of ventilation
	Days of renal replacement therapy

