#### PLUS, criteria for infection

- Initiation of a new antibiotic treatment course of  $\geq$  5 days, or
- A change in antibiotic treatment continued for  $\geq$  5 days, or
- Initiation of a new antibiotic treatment, or a change in antibiotic treatment, and death within 5 days, or
- Bacteraemia with a recognised intestinal pathogen.

New or changed antibiotic treatments must not be antibiotic prophylaxis, a change to achieve oral administration from intravenous antibiotics only, a change to reduce the spectrum of activity (targeted antibiotic treatment) or made due to antibiotic allergy only. New/changed antibiotics can include additional antibiotics, added to an ongoing treatment regimen. The first day of an eligible new/changed antibiotic treatment is called the antibiotic reference date. Inflammation 5 days either side of this antibiotic reference date can be assessed against the criteria for inflammation. A blinded endpoint committee will assess and classify data including but not limited to inflammation and antibiotic treatments to assign participants with treatment failure.

Once discharged, treatment failure requires re-admission to hospital and the in-patient criteria above to be met. Alternatively, they must have been admitted to hospital and have consumed antibiotics for > 48 hours prior to admission. Treatment failure cannot be assigned based on inflammation (fever, neutrophilia and CRP>100mg/L) detected within the 5 days after an operative procedure (surgical or radiological). Treatment failure can be assigned based on pre-operative inflammation and post-operative antibiotic changes. Treatment failure cannot be assigned due to evidence of inflammation or infection, as defined above, within the first 5 days of antibiotic treatment for the initial cIAI. If treatment

is extended beyond the intervention duration this should be considered a new antibiotic treatment course.

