Days of prescribed antibiotic therapy: Electronic medical records will be accessed to determine antibiotic (anti-bacterial) prescriptions in hospital and in the community where available. This data will be supplemented with self-reported antibiotic use at day 30, 90 and 180. Data on anti-fungal treatment will be collected to assess rates of fungal infections e.g., vulvo-vaginal candidiasis.

Others: All-cause mortality, length of hospital stay; re-admission and *C. difficile* infection will be assessed at day 180 after randomisation by review of hospital, medical records and interview with participants.

An episode of Acute Kidney Injury (Y/N): Increase in serum creatinine by  $\geq 0.3$  mg/dl ( $\geq 26.5 \mu$ mol/l) within 48 hours; or increase in serum creatinine to  $\geq 1.5$  times baseline, which is known or presumed to have occurred within the prior 7 days; or urine volume < 0.5 ml/kg/h for 6 hours (KDIGO Clinical Practice Guideline for Acute Kidney Injury).

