#### 10.2.3 Primary outcome analysis

The primary clinical outcome is treatment failure (Failure vs No failure) within 180 days of randomisation, as defined in Section 3.4. The number and proportion of participants experiencing treatment failure will be reported by randomised group and overall, as will the number of participants with complete outcome and covariate data. The primary analysis will model the log odds of treatment failure using a mixed effect logistic regression model, with randomised treatment group, the stratification factors (Post-operative vs Non post-operative cIAI, Source control vs No source control,

ICU care vs No ICU care), and other pre-specified prognostic baseline covariates included as fixed effects, and random intercepts for recruitment site/hospital. All participants with non-missing primary outcome data will be included in this model, with any missing baseline covariate data being imputed using an appropriate method prior to model fitting. Inference concerning the effectiveness of the intervention will be primarily based on the estimated conditional odds ratio, two-sided 95% confidence interval and p-value for allocation from the fitted primary analysis model. To aid interpretability, point estimates and appropriate two-sided 95% confidence intervals for the relative risk (cases/non-cases) and absolute risk reduction (based on the fitted primary analysis model) will be reported, with the fixed effect covariates in the model set to various representative values (i.e. marginal risk ratio and risk difference at representative values). Average marginal effects on both the risk ratio and risk difference scales will also be reported with appropriate two-sided 95% confidence intervals.

Several pre-specified sensitivity analyses of the primary outcome will be conducted to investigate the possible influence of non-adherence (via the estimation of alternative estimands that aim to account for non-adherence), and different assumptions about the missing outcome data (via analysis of data multiply imputed assuming outcome data are missing at random (MAR) and assuming various systematic departures from MAR).

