# Appendix 4 – Schedule of Procedures

#  +/- 7 days

	Routine care	Baseline	Day 30 	Day 90 	Day 180 
Medical assessments	X				
Blood tests (as part of routine care)	X				
Source control procedure	X				
C. difficile faeces testing	Х				
In patient antibiotic prescriptions	X				
Microbiological sampling	X				
Informed consent		X			
Eligibility assessment and randomisation		X			
Medical history and Demographics		Х			
EQ-5D-5L questionnaire		Х	Х	X	X
Resource use questionnaires			Х	X	X
Outpatient antibiotic use Questionnaires			Х	X	x
Adherence questionnaires			Х		
Source control/source of infection assessment		X			
Objective data -Antibiotic prescriptions -Antimicrobial resistance -Inflammatory markers -Mechanical ventilation -Readmission -Renal function -Vasoactive agent use			x	x	x
Objective data -C. difficile results -Renal replacement					x

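### Appendix 4 lets the final record collection close up to 7 days before the 180-day outcome period ends, and before a late treatment failure can be confirmed

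*Protocol*

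**What the plan says.** - **Horizon.** The trial summary and section 3.4 set the primary outcome over 180 days: "Treatment failure within 180 days of randomisation". Section 10.2.3 makes it binary: "The primary clinical outcome is treatment failure (Failure vs No failure) within 180 days of randomisation". The summary gives the other secondary outcomes the same span: "A range of secondary outcome measures (measured from day 0 to day 180".
- **Confirmation time.** Section 3.4 lists four infection criteria. Two need at least 5 days of treatment, a new course or "A change in antibiotic treatment continued for" that time. The third needs death within 5 days of a new or changed antibiotic. The fourth, bacteraemia with an intestinal pathogen, has no duration requirement. On timing of inflammation: "Inflammation 5 days either side of this antibiotic reference date can be assessed against the criteria for inflammation".
- **Collection schedule.** In Appendix 4 a ±7 day footnote is attached to the Day 30, Day 90 and Day 180 headings. The Day 180 column holds the questionnaires and also the record-based objective data, among them "Antibiotic prescriptions -Antimicrobial resistance -Inflammatory markers", readmission, mechanical ventilation, renal function, C. difficile results and renal replacement. No later column exists.
- **Other text.** Section 3.6 says that mortality, length of stay, re-admission and C. difficile "will be assessed at day 180 after randomisation by review of hospital, medical records and interview with participants", with no window.
- **Analysis set.** Section 10.2.3: "All participants with non-missing primary outcome data will be included in this model".

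**The concern.** A symmetric window suits a questionnaire, where a few days either way hardly change the answer. It does not suit the closing date of an event outcome. A record review on day 173 follows the schedule, yet days 174–180 lie inside the outcome period and have not happened. Even a review on day 180 exactly cannot show that a course started on day 177 or later reached 5 days.

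What is at stake is under-ascertainment that depends on when a site did its review and not on the outcome definition. A participant reviewed early with nothing found would not obviously be flagged as missing, so the planned sensitivity analyses for missing outcomes may not reach the problem. Record-based outcomes counted over the full period, such as antimicrobial, ventilation and renal replacement days, could lose up to 7 of 180 days for the same participants. Section 3.6 and Appendix 4 also disagree for re-admission and C. difficile: one gives day 180 with no window, the other day 180 ±7.

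**Working it through.** **1. The plan's own sample size (section 10.1).** Inputs: 50% v 40%, two-sided 5%, 90% power, 524 per arm, 10% attrition. The standard two-proportion formula gives 519 per arm (1038), against the stated 524 (1048), which is within 1%. With n per arm, d = p1 − p2 and p̄ the mean rate:

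power = Φ{[d√n − 1.96√(2p̄(1−p̄))] / √[p1(1−p1) + p2(1−p2)]}

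= Φ{[0.10 × 22.89 − 1.96 × 0.7036] / 0.70} = Φ(1.300) = 0.903.

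Attrition: 524/0.9 = 582.2, so 583 per arm and 1166 in total. The plan's figures reproduce.

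**2. Which course starts can be confirmed.** A course starting on day s reaches its fifth day on day s + 4. A review on day R can confirm starts up to day R − 4.

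- R = 173 (180 − 7, the earliest allowed): last confirmable start is day 169. Starts on days 170–180 are unseen or unconfirmed.
- R = 180: last confirmable start is day 176. Starts on days 177–180 are unconfirmed.
- R = 184 or later: all starts to day 180 can be confirmed on course length. Inflammation up to 5 days after a day-180 start runs to day 185.

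**3. Share of failures lost.** Let F(t) be cumulative failure, with F(180) = 0.50. The share lost is [F(180) − F(R − 4)] / F(180). The protocol gives no timing for treatment failure, so four assumptions are shown:

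- *Uniform:* F(t) = 0.5t/180.
- *Constant hazard:* F(t) = 1 − 0.5^(t/180).
- *Weibull:* half of failures by day 18, the relapse median in section 1, so F(18) = 0.25 and F(180) = 0.50; shape 0.38.
- *Lognormal:* fitted to the relapse median (18 days) and upper quartile (30 days) in section 1.

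Both arms' rates (50% and 40%) are reduced by the same share, and power is recomputed at 524 per arm.

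| Timing | All on day 173: lost, power | All on day 180: lost, power | Spread evenly over days 173–187: lost, power |
|---|---|---|---|
| Uniform | 6.1%, 0.869 | 2.2%, 0.891 | 2.4%, 0.890 |
| Constant hazard | 4.3%, 0.880 | 1.6%, 0.895 | 1.7%, 0.894 |
| Weibull | 1.7%, 0.895 | 0.6%, 0.900 | 0.7%, 0.900 |
| Lognormal | 0.04%, 0.903 | 0.01%, 0.903 | 0.01%, 0.903 |

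Worked case, constant hazard and day 173: F(180) − F(169) = 2.16 percentage points; 2.16/50 = 4.3%; rates become 47.8% v 38.3%; power 0.880. If the unconfirmed stretch is taken as a full 7 + 5 = 12 days, the uniform case becomes 12/180 = 6.7% with power 0.866.

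**4. How far to trust the timing assumptions.** The Weibull matches only the relapse median: it puts the quartiles of failures at about 2 and 65 days, against 13 and 30 in the cited cohort, so its late tail is too heavy for relapse. The lognormal describes relapse well, but relapse occurred in 17.3% of that cohort, while section 10.1 assumes at least 50% failure on a definition that is not confined to relapse. The true figure cannot be fixed from the protocol.

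**The case against.** The best case for the plan is that Appendix 4 says when a task is done and not which days the data cover. Every outcome is defined over 180 days, the data come from routine records that can be read back at any time, a blinded committee adjudicates, and details of data handling are left to a data management plan. Day 187 is as permissible as day 173. This has force: nothing prevents a site or the committee from completing an open episode. But nothing requires it either, and the last scheduled look may lawfully fall before the period ends. An analysis plan cannot recover records that were not collected.

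Three stronger readings are not supported.

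- *Late failures are scored as no failure.* A reader might infer this from the binary coding and the analysis set in section 10.2.3. The protocol does not say it; it has no rule for a record closed early. They may be scored that way.
- *Deaths and hospital stay are lost through the same window.* Appendix 4 has no row for mortality or length of stay. Section 3.6 places both at day 180, and deaths also come in through serious adverse event reporting (section 9.5).
- *The treatment comparison is biased towards one arm.* The window is the same in both arms. Differential bias would need review timing that differs by arm, and the protocol gives no reason to expect that.

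The objection that the size is small also stands.

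**Conclusion.** The point holds as a mismatch between the collection schedule and the outcome definition: a compliant final collection can precede day 180, and even a punctual one cannot confirm failures by course length or early death if the course starts from day 177. Failures by the bacteraemia criterion do not need the 5-day course.

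The expected consequence is mild under-ascertainment, similar in both arms, which would slightly shrink the absolute difference. With 50% v 40% true failure and 524 per arm, the extreme case of every review on day 173 costs between almost nothing and about 4% of failures (6–7% if failures were uniform in time), with power about 0.87–0.90 against 0.903. With reviews spread evenly over the window, the constant-hazard and Weibull cases lose 1.7% and 0.7%, with power about 0.89–0.90; uniform timing loses 2.4%, and the lognormal shows practically no loss. These figures assume equal loss in both arms, every unconfirmed failure counted as no failure, and timing curves that the protocol cannot verify. The case for acting rests on the very low cost of the correction, not on a large threat to the trial.

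**What to change.** In Appendix 4, keep ±7 days for the questionnaires only. Require the final record-based extraction on or after day 185, covering all records to day 180. Count antibiotic reference dates and events only up to day 180, and use later records solely to confirm course length, death within 5 days and inflammation within 5 days. Align the day-180 wording in section 3.6 with this.

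Cost: one footnote and a form instruction. The last participant's record review closes about 5 days later. No extra visits, tests or participants are needed.

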## iv. FUNDING AND SUPPORT IN KIND

FUNDER(S) and contact details	FINANCIAL AND NON FINANCIALSUPPORT GIVEN
National Institute of Health Research (NIHR)	Sole funder of research
Health Technology Assessment (HTA)	

## v. ROLE OF TRIAL SPONSOR AND FUNDER

The University of Leeds (UoL) is the Sponsor of the trial and employer of the Chief Investigator. This is an investigator-led multi-site trial. The study is managed and conducted by the Chief Investigator, with the UoL overseeing the activity to ensure appropriate regulatory and governance procedures are in place. The sponsor was not directly involved in the design of the trial.

The funder is the National Institute for Health and Care Research (NIHR). The funder undertook review of the trial design prior to contracting the research. The trial will be conducted as contracted without involvement of the sponsor except the funder will be consulted for approval if major amendments to design and conduct are planned after review by an independent DMEC and TSC.

Neither sponsor/funder will have input into data analysis/interpretation and manuscript writing. The funder will not control the final decision regarding any of these aspects of the trial.

